#### **9.4.3.5. Adverse Events of Special Interest**

Based on preclinical data generated to date, there is reason to believe that subjects will develop some level of thrombocytopenia. No human data have been generated yet to support this. Additionally, there is a chance for a "rebound" effect on platelets (potentially thrombocytosis) once the drug is discontinued, but human data have not been generated to support this effect. Subjects will be monitored closely and based on CTCAE grading of thrombosis will be reported as AEs as appropriate.

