## APPENDIX F. INTERNATIONAL WORKING GROUP RESPONSE CRITERIA FOR MYELODYSPLASTIC SYNDROME

Category	Response Criteria (Responses Must Be at Least 4 Weeks in Duration)
Complete remission (CR)	Bone marrow: $\leq 5\%$ myeloblasts with normal maturation of all cell lines Persistent dysplasia will be noted Peripheral blood: Hemoglobin (Hgb) $\geq 11$ g/dL, Platelets $\geq 100 \times 10^9/L$ , Neutrophils $\geq 1.0 \times 10^9/L$ Blasts 0%
Partial remission (PR)	All CR criteria if abnormal before treatment, except: Bone marrow blasts decreased by $\geq 50\%$ over pretreatment but still $> 5\%$ Cellularity and morphology not relevant
Marrow CR	Bone marrow: $\leq 5\%$ myeloblasts and decrease by $\geq 50\%$ over pretreatment Peripheral blood: if HI responses, they will be noted in addition to marrow CR
Stable disease (SD)	Failure to achieve at least PR, but no evidence of progression for $> 8$ weeks
Treatment failure	Death during treatment Disease progression characterized by worsening of cytopenias, increase in % of bone marrow blasts, or progression to a more advanced MDS FAB subtype than pretreatment
Disease progression (PD)	For patients with: 
 
- Less than 5% blasts: <math>\geq 50\%</math> increase in blasts to <math>> 5\%</math> blasts
 
- 5%-10% blasts: <math>\geq 50\%</math> increase in blasts to <math>> 10\%</math> blasts
 
- 10%-20% blasts: <math>\geq 50\%</math> increase in blasts to <math>> 20\%</math> blasts
 
- 20%-30% blasts: <math>\geq 50\%</math> increase in blasts to <math>> 30\%</math> blasts
 
 Any of the following: 
 
- At least 50% decrement from maximum remission/response levels in granulocytes or platelets
 
- Reduction in Hgb concentration by <math>\geq 2</math> g/dL
 
- Transfusion dependence
 

Disease transformation	Transformation to AML (30% or more blasts)
Relapse after CR or PR	At least 1 of the following: 
 
- Return to pretreatment bone marrow blast %
 
- Decrement of <math>\geq 50\%</math> from maximum remission/response levels in granulocytes or platelets
 
- Reduction in Hgb concentration by <math>\geq 1.5</math> g/dL or transfusion dependence
 

CYTOGENETIC RESPONSE	
Complete	Disappearance of the chromosomal abnormality without appearance of new ones
Partial	At least 50% reduction of the chromosomal abnormality

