### 7.3.3.2. Best Overall Response and Objective Response Rate

#### 7.3.3.2.1. Altering the Natural History of the Disease

For MDS, BOR based on altering the natural history of the disease is the best response recorded before and including the first progression, which consists of treatment failure, PD, disease transformation, and relapse after CR or PR, in the order of CR, PR, marrow CR, SD, and progression. In the case of SD, measurements must meet the SD criterion at least once on or after Day 24. When analysis requires the confirmation of CR, PR, or marrow CR, responses must be at least 4 weeks in duration and the rule in [Table 3](#) should be applied.

**Table 3: Confirmation of Complete Remission, Partial Remission, and Marrow Complete Remission for Myelodysplastic Syndrome**

First Assessment	Subsequent Assessment at 4 or More Weeks Later	Confirmed Response
CR	CR	CR
PR	PR or CR	PR
Marrow CR	Marrow CR, PR, or CR	Marrow CR

A subject is considered a responder if the subject has a best overall response of CR.

Objective response rate for MDS is defined as the proportion of responders based on altering the natural history of the disease. Subjects who do not have sufficient baseline or on-study response assessment information to be adequately assessed for response status will be included in the denominators in the calculations of ORR.

Non-confirmed BOR will be summarized descriptively, and the ORR will be estimated with its 95% CI. Best confirmed response of CR, PR, and marrow CR will be summarized descriptively. The confirmed ORR will be estimated with its 95% CI. Confidence intervals will be calculated based on the exact method for binomial distributions.

[figure not shown]

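### SAP Table 3 for MDS is order-dependent: marrow CR then CR is a confirmed marrow CR, but CR then marrow CR is no confirmed response, even when the marrow CR definition was met at both assessments

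*SAP*

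**What the plan says.** SAP 7.3.3.2.1 takes the MDS best overall response (BOR) no further than the first progression. It defines progression and the ranking as follows: "which consists of treatment failure, PD, disease transformation, and relapse after CR or PR, in the order of CR, PR, marrow CR, SD, and progression". On confirmation it says "When analysis requires the confirmation of CR, PR, or marrow CR, responses must be at least 4 weeks in duration and the rule in", pointing to Table 3.

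Table 3 pairs a first assessment with a second one, headed "Subsequent Assessment at 4 or More Weeks Later". A first CR is confirmed only by CR. A first PR is confirmed by PR or CR. A first marrow CR is confirmed by "Marrow CR, PR, or CR".

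Two further SAP sentences fix what the table can affect. The responder definition is "A subject is considered a responder if the subject has a best overall response of CR". The confirmed categories are also reported on their own: "Best confirmed response of CR, PR, and marrow CR will be summarized descriptively".

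Protocol Appendix F defines marrow CR by the marrow: myeloblasts at or below 5% and down by at least 50% from pretreatment. Blood counts are not part of it: "Peripheral blood: if HI responses, they will be noted in addition to marrow CR". CR adds blood thresholds (Hgb at least 11 g/dL, platelets at least 100, neutrophils at least 1.0, no blasts). Every category must last at least 4 weeks.

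**The concern.** Marrow CR does not depend on blood counts. A subject in CR whose blasts fell by at least 50%, and who at the next assessment keeps the marrow result but loses a blood threshold, has therefore met the marrow CR definition at both assessments. Table 3 accepts a CR as evidence for marrow CR when it comes second, but not when it comes first. The subject with the deeper first response is then recorded below one whose first response was only marrow CR.

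The sequence is plausible in this study. Protocol 9.4.3.5 says "there is reason to believe that subjects will develop some level of thrombocytopenia", Protocol 1.6.4 names myelosuppression as the main dose-limiting toxicity of azacitidine, and Protocol 5.4.1 makes provision for TG C and TG D subjects whose marrow has responded but whose counts need to recover. At stake is the accuracy of the best-confirmed-response summary for MDS.

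**Working it through.** The plan states no figure on this point, so there is none to reproduce. The check is to apply the table as written.

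**1. All nine ordered pairs** (entries are the confirmed response):

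| First assessment | Later CR | Later PR | Later marrow CR |
|---|---|---|---|
| CR | CR | none | none |
| PR | PR | PR | none |
| Marrow CR | marrow CR | marrow CR | marrow CR |

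Six pairs are confirmed and three are not. The six are exactly those where the second assessment ranks equal to or above the first in the BOR order.

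**2. The three missing pairs are not alike.** Under Appendix F, PR leaves blasts above 5%. In CR then PR, the subject is not in PR at the first visit. In PR then marrow CR, the subject is not in marrow CR at the first visit. Only in CR then marrow CR can the lesser category have been met at both.

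**3. An illustrative record** (values assumed, thresholds from Appendix F). Pretreatment blasts are 12%.

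- First assessment: blasts 3%, Hgb 11.4, platelets 110, neutrophils 1.3. This is CR.
- Next assessment, 4 weeks later: blasts 3%, Hgb 10.6, platelets 70, neutrophils 1.3, no transfusion dependence. This is marrow CR.
- Blast fall at both: (12 − 3)/12 = 75%, above the required 50%.
- Platelet fall: (110 − 70)/110 = 36%, below the 50% limit for relapse or progression.
- Hgb fall: 11.4 − 10.6 = 0.8 g/dL, below the limits of 1.5 (relapse) and 2 (progression).

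If progression comes next, or assessments end, Table 3 gives no confirmed response. The same two results in reverse order give a confirmed marrow CR.

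**4. Longer sequences**, under the table as written and with an added row (CR, then marrow CR = marrow CR):

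| Sequence | As written | With the row |
|---|---|---|
| CR, marrow CR | none | marrow CR |
| CR, marrow CR, progression | none | marrow CR |
| CR, marrow CR, marrow CR | marrow CR | marrow CR |
| CR, marrow CR, CR (any later visit may confirm) | CR | CR |
| CR, CR, marrow CR | CR | CR |

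For CR, marrow CR, CR, the table as written gives only marrow CR if just the next assessment may confirm. The SAP does not say which reading applies.

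**5. Effect on the ORR.** There are 4² + 4³ + 4⁴ = 336 sequences of two to four assessments drawn from CR, PR, marrow CR and SD. With any later assessment allowed to confirm, the added row changes confirmed-CR status in 0 of them. Since the MDS responder is CR only, the confirmed ORR does not move. The non-confirmed ORR does not use Table 3.

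**6. Size per subject.** The documents do not give the number of MDS subjects. One affected subject is 1/10 = 10 points, 1/15 = 6.7 points or 1/30 = 3.3 points of an assumed set of 10, 15 or 30.

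**7. Why the row needs a condition.** CR requires blasts at or below 5% but no 50% fall. From 6% to 4%, for example, is a fall of (6 − 4)/6 = 33%, which does not meet marrow CR.

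**The case against.** The strongest reply is that the study's own schedule closes most of the gap. MDS status is due every 4 weeks on treatment, by blood or marrow (Protocol 7.6 and Table 7; SAP 7.3.3.1), again at end of treatment, and every 8 to 9 weeks in follow-up for subjects who stop without progression. One more marrow CR at least 4 weeks after the first confirms marrow CR under the existing third row, and a return to CR also gives a confirmed response. This stands. A reader might infer that any MDS subject whose marrow holds while counts fall gets no confirmed response; the documents do not support that.

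Larger falls are also outside the gap. A platelet or granulocyte fall of 50% or more, an Hgb fall of 1.5 g/dL or more, or transfusion dependence is relapse after CR in Appendix F, and the SAP counts that as progression.

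It can further be said that the table is deliberately one-directional, that no defined rate moves, and that the subject still appears as CR in the non-confirmed BOR and in Listing 2.6.1. One-directional confirmation explains why the CR is not confirmed. It does not explain why a marrow CR met at both visits is not confirmed either.

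What remains is the subject with CR, then marrow CR, then progression or no further qualifying assessment. Marrow examinations can be about two months apart (Protocol 7.6), and mean participation is about 6 months (Protocol 4.4), so this can occur.

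**Conclusion.** The point holds in a narrow form. Table 3 gives an order-dependent result that conflicts with the Appendix F definition, and no other text in either document resolves it. It can lower the descriptive summary of best confirmed response in MDS, by 6.7 points per affected subject if the set has 15 subjects. That 15 is an assumption borrowed from the protocol's TG D1 futility rule.

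Two stronger readings are not supported:

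- **A quantified downward bias from the drug's blood effects.** The protocol expects thrombocytopenia but gives no rate for falls that lose CR yet stay short of relapse, and none for subjects left without a further qualifying assessment.
- **An effect on stopping for futility.** Protocol 9.6 counts CR or marrow CR among the first 15 MDS subjects in TG D1 and does not mention confirmation; SAP 10.1 does not refer to Table 3.

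The confirmed and non-confirmed ORR are unaffected. Low priority.

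**What to change.** Add a row to SAP Table 3: first assessment CR, subsequent assessment marrow CR at 4 or more weeks, confirmed response marrow CR, provided marrow blasts were at least 50% below pretreatment at both assessments. In the same edit, state the confirmed result (or none) for CR then PR and for PR then marrow CR, and say whether any later assessment or only the next one may confirm.

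The cost is one table edit and its programming. It needs no new data, because investigator-assessed response is already recorded at each assessment visit and marrow pathology results are already captured in the eCRF.

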### 2.2.2. Secondary Endpoints

- **Parts 1 and 2:** Tumor response rates in those subjects with measurable disease or spleen volume changes as determined by investigator assessment of response per disease-specific guidelines.
  - Solid tumors: Objective response rate (ORR), defined as the percentage of subjects having complete response (CR) or partial response (PR) will be determined by the investigator assessment of radiographic disease assessments per RECIST v1.1.
  - Acute myeloid leukemia (AML)/myelodysplastic syndrome (MDS): ORR, defined as the proportion of subjects who achieve CR or complete remission with incomplete hematologic recovery (CRi) per the International Working Group Response Criteria for Acute Myeloid Leukemia or the International Working Group Response Criteria for MDS, as applicable.
  - MF: Change and percentage change in spleen volume reduction (SVR) as measured by magnetic resonance imaging (MRI; computed tomography [CT] scan in subjects who are not a candidate for MRI or when MRI is not readily available) at Week 12 when compared with baseline.
- **Parts 3 and 4:** Tumor response rates in those subjects with measurable disease as determined by investigator assessment of response per disease-specific guidelines.
  - Small cell lung cancer (SCLC): ORR, defined as the percentage of subjects having CR or PR will be determined by the investigator assessment of radiographic disease assessments per RECIST v1.1.
  - AML/MDS: ORR, defined as the proportion of subjects who achieve CR or CRi per the International Working Group Response Criteria for Acute Myeloid Leukemia or the International Working Group Response Criteria for MDS, as applicable.
- PK parameters of INCB059872 in plasma:  $C_{max}$ ,  $T_{max}$ ,  $C_{min}$ ,  $AUC_{0-t}$ ,  $t_{1/2}$ , and  $Cl/F$ .

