#### **9.6. Interim Analysis**

In Part 4, a stopping rule for futility is planned for each combination dose expansion treatment group. The futility analyses for combination TGs will be conducted when 15 subjects for each disease type have been treated and evaluated for response or have permanently discontinued study treatment because of disease progression, withdrawal of consent, or death. The futility

analyses for TG D1 will be conducted when the first 15 subjects with AML or when the first 15 subjects with MDS have been treated. Combination TG C1 will be terminated for futility if  $\leq 1$  of the 15 subjects responded (ie, CR, CRi, MLFS) based on assessments provided by investigator. Combination TG D1 will terminate enrollment for subjects with AML if  $\leq 2$  of the first 15 AML subjects responded (ie, CR, CRi, MLFS) or will terminate enrollment for subjects with MDS if  $\leq 2$  of the first 15 MDS subjects responded (ie, CR or marrow CR), based on assessments provided by investigator. Combination TG E1 will be terminated for futility if  $\leq 1$  of the 15 subjects responded (ie, CR or PR) based on assessments provided by investigator.

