### 2.3.2. Secondary Endpoints

- **Parts 1 and 2:** Tumor response rates in those subjects with measurable disease or spleen volume changes as determined by investigator assessment of response per disease-specific guidelines.
  - Solid tumors: ORR, defined as the percentage of subjects having CR or PR will be determined by the investigator assessment of radiographic disease assessments per RECIST v1.1.
  - AML/MDS: ORR, defined as the proportion of subjects who achieve CR or CRI per the IWG Response Criteria for AML or the IWG Response Criteria for MDS, as applicable.
  - MF: Change and percentage change in spleen volume as measured by MRI (CT scan in subjects who are not a candidate for MRI or when MRI is not readily available) at Week 12 when compared with baseline.
- **Parts 3 and 4:** Tumor response rates in those subjects with measurable disease as determined by investigator assessment of response per disease-specific guidelines.
  - SCLC: ORR, defined as the percentage of subjects having CR or PR will be determined by the investigator assessment of radiographic disease assessments per RECIST v1.1.
  - AML: ORR, defined as the proportion of subjects who achieve CR or CRI per the IWG Response Criteria for AML.
- PK parameters of INCB059872 in plasma:  $C_{max}$ ,  $T_{max}$ ,  $C_{min}$ ,  $AUC_{0-t}$ ,  $t_{1/2}$ , and  $Cl/F$ .

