### **7.3.3. Myelodysplastic Syndrome**

#### **7.3.3.1. Response Assessment**

Disease assessment for MDS subjects will be performed following the IWG Response Criteria for MDS ([Cheson et al 2006](#)). The investigator's assessment will be used to determine responses and will be logged on the eCRF. The schedule for disease assessment will be at screening, every 4 weeks during the study treatment, at the EOT visit, and every 8 to 9 weeks during the disease status follow-up.

Response status per investigator's assessment for MDS will be recorded in terms of 3 aspects: (1) altering the natural history of the disease, (2) cytogenetic response, and (3) hematologic improvement. For altering the natural history of the disease, response status will be recorded at each response assessment visit as CR, PR, marrow CR, SD, PD, treatment failure, disease transformation, or relapse after CR or PR. For cytogenetic response, response status will be recorded at each response assessment visit as CCyR, PCyR, or NA. For hematologic improvement, response status will be recorded at each response assessment visit as HI-E, HI-P, HI-N, progression or relapse after hematologic improvement, or NA. Refer to Appendix F in the Protocol for the summarized description of the IWG Response Criteria for MDS.

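### For MDS, the D1 futility look counts CR or marrow CR while ORR counts CR only, and no final rate with an interval is planned for the response that decides enrolment

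*SAP*

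**What the plan says.** **Endpoint.** Protocol 2.2.2 gives a single definition for both diseases, using the AML or MDS criteria as applicable: "AML/MDS: ORR, defined as the proportion of subjects who achieve CR or CRi per the International Working Group Response Criteria". SAP 2.3.2 repeats it for Parts 1 and 2 ("AML/MDS: ORR, defined as the proportion of subjects who achieve CR or CRI per the IWG Response Criteria for AML"). For Parts 3 and 4, SAP 2.3.2 lists AML only.

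**MDS categories.** Protocol Appendix F has no CRi. SAP 7.3.3.1 has none either; MDS status is "recorded at each response assessment visit as CR, PR, marrow CR, SD, PD, treatment failure, disease transformation, or relapse after CR or PR".

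**Analysis.** SAP 7.3.3.2.1 ranks best overall response (BOR) "in the order of CR, PR, marrow CR, SD, and progression" and then states: "A subject is considered a responder if the subject has a best overall response of CR". ORR and confirmed ORR get exact 95% CIs. Marrow CR appears only in the descriptive BOR and best-confirmed-response summaries.

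**Futility.** Under protocol 9.6, TG D1 stops enrolling MDS if 2 or fewer of the first 15 "MDS subjects responded (ie, CR or marrow CR), based on assessments provided by investigator". SAP 3 and SAP 10.1 give one D1 rule, CR or CRi in 15 subjects, with no MDS version.

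**Reporting unit.** SAP 5.2 and SAP Appendix A combine TG D and TG D1 as Group D, with no split by disease stated. Monotherapy efficacy, by contrast, is split by tumor type.

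**Timing.** SAP 2.1 bases the SAP on Amendment 5 and keeps it in force for later amendments unless superseded. Amendment 6 brought MDS into TG D. SAP Table 6 lists only the original version.

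**The concern.** The D1 MDS go/no-go decision rests on one response and the reported ORR on a narrower one. Marrow CR counts towards continuing enrolment but not towards ORR. A reader of the final report who wants to know whether the response that kept the MDS cohort open held up will find no planned estimate of it with an interval. Because Group D is pooled, that reader may not find an MDS figure at all.

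Appendix F makes a gap between the two responses plausible. CR for MDS requires recovery of hemoglobin, platelets and neutrophils; marrow CR does not. The sponsor's stated reason for widening the AML futility response in Amendment 6 was response without platelet recovery, attributed to the drug's on-target effect. If MDS behaves the same way, marrow CR without CR is what one would expect to see.

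There is also a plain wording error: the protocol endpoint names a category that does not exist for one of the two diseases it covers.

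**Working it through.** **Plan's own figures.** The documents give no target response rate and no operating characteristics for the futility rule, so there is no stated figure to reproduce on this point.

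**Step 1. Which definitions differ in count?**

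| Source | Counts as response in MDS | Effective count |
|---|---|---|
| Protocol 2.2.2; SAP 2.3.2 (Parts 1 and 2) | CR or CRi | CR, since CRi is not an MDS category |
| SAP 7.3.3.2.1 | CR | CR |
| Protocol 9.6 (D1 MDS) | CR or marrow CR | CR + marrow CR |
| SAP 3 and 10.1 (all of D1) | CR or CRi | No MDS rule; CR if applied to MDS |

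In practice there are two counts: CR, and CR plus marrow CR.

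**Step 2. Lowest ORR compatible with passing.** Continuing needs at least 3 of 15. Three marrow CRs and no CR satisfy this, with ORR 0/15. The exact 95% upper limit is 1 − 0.025^(1/15) = 21.8%. If both used the same definition, the lowest rate at a passed look would be 3/15 = 20.0% (95% CI 4.3 to 48.1%).

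**Step 3. How likely is a low ORR after passing?** Let c be the CR rate, m the marrow CR rate and q = 1 − c − m. Both rates are assumptions. I hold c + m at 30% and vary the split.

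- P(stop) = q^15 + 15(0.30)q^14 + 105(0.30)²q^13 with q = 0.70: 0.0047 + 0.0305 + 0.0916 = 0.127. P(pass) = 87.3%.
- P(pass, 0 CR) = (1−c)^15 − [q^15 + 15m·q^14 + 105m²·q^13].
- P(pass, exactly 1 CR) = 15c·{(1−c)^14 − [q^14 + 14m·q^13]}.

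For c = 10% and m = 20%: 0.2059 − 0.0658 = 0.140 with no CR, plus 1.5 × (0.2288 − 0.0339) = 0.292 with one CR, giving 0.432. Expected counts in 15 are 15 × 0.30 = 4.5 futility responders and 15 × 0.10 = 1.5 CRs.

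| CR / marrow CR (assumed) | Pass, CR or marrow CR | Pass with 0 CR | Pass with at most 1 CR (ORR ≤ 6.7%) | Pass if only CR counted |
|---|---|---|---|---|
| 5% / 25% | 87.3% | 37.0% | 70.5% | 3.6% |
| 10% / 20% | 87.3% | 14.0% | 43.2% | 18.4% |
| 20% / 10% | 87.3% | 1.0% | 8.1% | 60.2% |

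The last column shows that the choice of response also decides how strict the look is.

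**Step 4. Can the futility rate be rebuilt from the planned tables?** Only roughly. BOR ranks PR above marrow CR, so a subject with marrow CR at one visit and PR at another falls in the PR row. Adding the CR and marrow CR rows would miss that subject, and no interval is attached to the sum.

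**The case against.** The best defence is that the difference is a design choice. Protocol 5.4.1 groups CR and marrow CR for MDS with at least MLFS for AML as a bone marrow blast response. The Amendment 6 rationale explains why MLFS was added to AML futility, and that amendment also brought MDS into protocol 9.6. AML shows the same pattern: MLFS counts for futility but not in the ORR of SAP 7.3.2.2.1. A lenient activity screen beside a stricter reported ORR is legitimate, especially in an exploratory study with no efficacy hypothesis. This stands, although neither document states the intent for MDS.

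Three stronger readings are tempting and are not supported:

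- *MDS response has three competing counts, and the SAP silently narrowed the endpoint.* Since CRi is not an MDS category, CR or CRi and CR give the same count. The SAP applies the protocol endpoint in the only way available, so the empty SAP 11.1 is not a serious omission on this definition.
- *Marrow CR is never reported.* It is tabulated within BOR and best confirmed response, and responses are listed by subject. What is missing is the combined rate and its interval.
- *D1 MDS will pass and then report an ORR near zero.* The SAP specifies no separate D1 MDS ORR, and the likelihood depends on a CR to marrow CR split that the documents do not give. A marrow CR at the look can also become a CR later, and the final denominator need not be 15.

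**Conclusion.** The point holds as a modest reporting and consistency gap. The protocol endpoint names a category that MDS does not have. The response that decides D1 MDS enrolment has no planned final rate with an interval. The SAP was not updated after MDS entered TG D: it has no MDS endpoint for Parts 3 and 4, no MDS futility rule and no disease split in Group D.

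That the look can be passed with an ORR of 0/15 (95% CI 0 to 21.8%) follows from the definitions alone. The probability of at most one CR among 15 together with a pass ranges from 8.1% to 70.5% over the assumed splits of a 30% combined rate. It therefore should not be read as a prediction. These figures describe the first 15 MDS subjects at the look, treated as independent.

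**What to change.** 1. Protocol 2.2.2 and SAP 2.3.2: state that ORR for MDS is CR per Appendix F, and add MDS to the SAP's Parts 3 and 4 list.
2. SAP 7.3.3.2.1: keep ORR as CR and add the proportion with CR or marrow CR, with an exact 95% CI. Define the numerator so that it matches the futility count, since PR outranks marrow CR in BOR, and say whether confirmed or non-confirmed responses are used.
3. SAP 5.2 and Appendix A: present Group D efficacy separately for AML and MDS.
4. SAP 3 and 10.1: reconcile with the futility definitions in protocol 9.6. If the futility response is deliberately broader than ORR, say so.

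The cost is wording and an extra table row, with no new data collection. The MDS subgroup will be small, so the added interval will be wide; at 3/15 it runs from 4.3% to 48.1%.
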